9.1. Sample Size Justification

Sample size: 250 patients

Within a descriptive study, the number of participants required depends on the desired accuracy for observed frequencies. With 236 patients enrolled in the cohort, a 95% confidence interval

size of ± 6.0% will be obtained for a attended frequency of mRS ≤ 2 at 90 days of 32,6% (rate observed in [name]). In addition, even with 5% of patients lost to follow-up, we still dispose of an accuracy of at least ±6% for observed frequencies (Effectiveness and safety parameters).

9.2. Statistical Analysis

The objective of the statistical analyses is to support the demonstration that the Sofia/Sofia Plus Catheters used as aspiration catheter can reach Clinical outcome defined as mRS ≤ 2 at 90 days. All confidence intervals presented will be two-sided. All statistical tests will be two-tailed with a significance level of 0.05. Descriptive statistics will be provided. This includes the number of observations, mean, median, standard deviation, minimum and maximum for continuous variables and counts and percent for discrete variables. Results collected at multiple visits will be summarized at each visit. Summaries for all measures will include all observed data for each visit. All endpoints will be evaluated for the SOFIA and SOFIA Plus Catheter separately.

9.2.1. Definition of Analysis Samples

All primary and secondary Effectiveness and safety outcome measures will be analyzed under both the intent-to-treat (ITT) and per-protocol (PP) principles.

a) Intent to Treat Sample

The ITT sample includes all participants who are enrolled.

b) Per Protocol Sample

The per-protocol sample will include all participants that do not have the following protocol violations or deviations:

1) Eligibility violation

2) No Sofia/Sofia Plus treatment performed

3) mRS primary effectiveness only: missing 90-day outcome (not including missing due to death prior to the 90 days)

9.2.2. Effectiveness

Primary Endpoints

The primary effectiveness variable is the Clinical outcome defined as mRS \leq 2 at 90 days (assessment performed by an independent neurologist)

The proportion of patients who are successful based on each criterion will be calculated. Estimates of the group differences and their 95% confidence intervals will be calculated. Multiple ordinal logistic regression analysis estimated the effect of treatment and tested for the interaction of time to reperfusion with treatment. The effect of treatment as a risk difference on reaching independence (mRS score, 0-2) will be computed as a function of time to reperfusion. Whenever appropriate, calculations will be adjusted for age, National Institutes of Health Stroke Scale score, previous stroke, atrial fibrillation, diabetes mellitus, smoking status and intracranial arterial terminus occlusion. For missing data (patients who were lost to follow-up) the mRS scores at 90 days will be assigned using multiple imputations, worst case scenario (mRS = 6), and best case scenario (mRS=0).

9.2.3. Safety

The safety variables:

- The occurrence of major neurological events (stroke, intracranial hemorrhage, intracerebral hemorrhage, etc.) prior to discharge
- Devices and procedure related adverse events within 90 days of follow up
- Occurrence of embolization in previously uninvolved (or new) territories (ENT) as seen on the final control angiogram at the end of the procedure
- Occurrence of symptomatic intracranial hemorrhages (sICH) within 24 hours
- Occurrence of intracranial vessel damages at the end of the procedure.

Descriptive statistics will be provided for each safety variable. Estimates of the group differences and their 95% confidence intervals will be calculated.

9.2.4. Recanalization:

- Proportion of patients having complete recanalization (TICI ≥ 2b) just after first line aspiration treatment compared to historic controls based on published RCTs*
- Proportion of patients having complete recanalization (TICI ≥ 2b) after thrombectomy using an additional device
- Time from groin puncture to complete recanalization (TICI ≥ 2b) in patients after first line aspiration treatment (SESAME).
- Time from groin puncture to recanalization (TICI ≥ 2b) after thrombectomy using an additional device
- Time from CT-scan/MRI at the institution to groin access
- Time from symptom onset to CT-scan/MRI

* assessed by an imaging core lab.

Descriptive statistics will be provided for each recanalization measurement variable. Estimates of the group differences and their 95% confidence intervals will be calculated.

9.2.5. Clinical endpoints / quality of life:

- NIHSS score at 24 hours
- NIHSS score at discharge
- Quality of Life at 90 days

Descriptive statistics will be provided for quality of life variables and changes in variable values. Estimates of the group differences and their 95% confidence intervals will be calculated.

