	Statistical test will be	performed with a type I error risk of 5%.		
	The rate of events for	which a date of onset has been collected will be		
	described by a surviva	al curve according to Kaplan-Meier method and the		
	associated Kaplan-Me	ier estimators will be calculated.		
	An interim analysis wil	vsis will be performed after 50 patients are enrolled.		
Anticipated Timelines	FPI	October 2017		
	LPI	April 2021		
	FPO	January 2018		
	LPO	July 2021		
	Database lock	September 2021		
Financing	Financial support for the SESAME study will be pro MicroVention Europe, a			
	French limited liability company, with capital of 40 000€, registered with			
	the Registry of Commerce and Companies in Versailles under number 440			
	775 674 RCS, with registered address at [name],			
	[name], France.			

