5.5. Procedure

The SOFIA[™]/ SOFIA[™] PLUS Catheter will be used in removal/aspiration of emboli and thrombi following the CE marked Instructions For Use. Enrollment into the study does not change the routine care at the site provided to the patient requiring mechanical thrombectomy treatment. The time of the following events will be recorded for each patient:

- Index stroke symptom onset
- Hospital admission
- Arterial puncture for endovascular intervention
- Pre-procedure TICI score
- Start of aspiration by the SOFIA[™]/ SOFIA[™] PLUS
- End of aspiration by the SOFIA[™]/ SOFIA[™] PLUS
- Time of first TICI 2b or 3
- If an adjunctive treatment is used, time and TICI score after SOFIA[™]/ SOFIA[™] PLUS Reperfusion Catheter has been used
- Last angiogram taken after all treatments at the end of the procedure.

Additionally, the following information will be recorded:

- Location and length of occlusion
- The final TICI after all adjunctive treatments
- Ancillary device and/or adjunctive treatment trade mark and model
- Intraprocedural complications
- Presence of vasospasm (time of onset, vessels involved, time resolved)
- Evidence of clot migration or embolization

- Dissections/ perforations
- Devices deficiencies, malfunction, complaints (including 2nd line devices in case of aspiration failure)
- Antiplatelet therapy regimen
- Sedation

Those patients with improving neurological status prior to endovascular intervention may or may not undergo mechanical thrombectomy at the discretion of the treating physician.

The definition of rapid improvement that leads to foregoing endovascular intervention is at the discretion of the Investigator based on clinical judgment regarding risks versus benefits.

Those patients excluded according to the selection criteria but treated with a SOFIATM / SOFIATM PLUS Catheter will be considered as intent to treat patients.

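### Time to recanalization is summarised only among patients who recanalize, so the result behind the speed aim leaves out aspiration failures

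*Protocol*

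**What the plan says.** Section 9.2.4 lists two procedural times to recanalization: "Time from groin puncture to complete recanalization (TICI ≥ 2b) in patients after first line aspiration treatment (SESAME" and "Time from groin puncture to recanalization (TICI ≥ 2b) after thrombectomy using an additional device". The analysis is one sentence: "Descriptive statistics will be provided for each recanalization measurement variable". Estimates of group differences with confidence intervals are added. No rule covers a patient who never reaches TICI ≥2b.

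Section 5.5 records the clock time of arterial puncture, of the start and end of aspiration, and of the last angiogram. It also records "Time of first TICI 2b or 3" and, if adjunctive treatment is used, the time and TICI score after the SOFIA catheter.

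The same list in 9.2.4 includes "Proportion of patients having complete recanalization (TICI ≥ 2b) just after first line aspiration treatment compared to historic controls based on published RCTs", and the corresponding proportion after an additional device.

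The synopsis (Statistical Methodology) says that the rate of events for "which a date of onset has been collected will be" described by a survival "curve according to Kaplan-Meier method and the" associated estimators. It states no censoring rule and does not say how death is handled. Sections 9.2.3 and 9.2.7 give safety endpoints descriptive statistics and adverse events a number and percent of patients. For repeated measures, section 9.2 says "Summaries for all measures will include all observed data for each visit".

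**The concern.** Speed stands beside safety and effectiveness in the study purpose (synopsis), in the introduction (section 3) and in the rationale (4.4). The endpoint meant to support it has a value only where the procedure worked. A patient in whom aspiration fails leaves the aspiration time and either enters a separate summary after another device or has no time at all.

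Such failures are expected. Section 5.6 provides for switching to other techniques, and section 3 reports that adjunctive or rescue procedures were needed more often with aspiration first than with stent retrievers. The patients who drop out of the aspiration time are therefore those in whom the first-line strategy was slowest or did not work. A short median among successes could go with a low success rate, and the number would still read as fast recanalization.

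A second, smaller matter is the Kaplan-Meier statement for dated events. In ordinary use for a non-fatal event, deaths are censored, which overstates the event's cumulative risk.

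**Working it through.** **The protocol's own figure.** It gives none for recanalization time or event curves. Its only planning figure is for the primary endpoint (9.1): 1.96 × √(0.326 × 0.674 / 236) = 0.0598, which agrees with the stated ±6.0%. It does not bear on this point.

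**Step 1: who has a value.**

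| Patient | Aspiration time | Additional-device time |
|---|---|---|
| TICI ≥2b by aspiration alone | yes | no |
| TICI ≥2b only after an additional device | no | yes |
| TICI ≥2b never reached | no | no |

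The aspiration time is therefore a summary of the first row only.

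**Step 2: what conditioning on success can hide.** The documents give no success share and no time distribution, so the inputs are assumptions: share s recanalized by aspiration from 50% to 90%, and times among successes lognormal with median 30 min and log-SD 0.6. If F is the distribution among successes, the proportion of all patients recanalized by aspiration at time t is s × F(t). Half of all patients are reached when F(t) = 0.5/s, so t = 30 × exp(0.6 × z), where z is the standard normal quantile of 0.5/s.

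| s | 0.5/s | z | Median among successes | All-patient median |
|---|---|---|---|---|
| 90% | 0.556 | 0.140 | 30 min | 32.6 min |
| 80% | 0.625 | 0.319 | 30 min | 36.3 min |
| 70% | 0.714 | 0.566 | 30 min | 42.1 min |
| 60% | 0.833 | 0.967 | 30 min | 53.6 min |
| 50% or below | ≥1 | – | 30 min | not reached |

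The middle column stays at 30 min while the experience of the whole cohort ranges from slightly slower to never reaching the halfway point. These figures are for recanalization by aspiration alone; rescued patients count as not reached.

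**Step 3: Kaplan-Meier for dated non-fatal events.** Assumed inputs: true 90-day cumulative incidence E of 5–20%, death without the event D of 10–25%, constant cause-specific hazards, deaths censored. The total cumulative hazard is H = −ln(1 − E − D), the event part is λ = H × E/(E + D), and the Kaplan-Meier risk is 1 − exp(−λ).

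- E = 5%, D = 10%: H = 0.1625, λ = 0.0542, risk 5.27%, excess 0.27 points.
- E = 10%, D = 10% to 25%: risk 10.56% to 11.58%, excess 0.56 to 1.58 points.
- E = 20%, D = 25%: H = 0.5978, λ = 0.2657, risk 23.33%, excess 3.33 points.
- A 24 h event with E = 5% and early deaths of 1% to 5%: risk 5.03% to 5.13%, excess at most 0.13 points.

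**The case against.** Conditioning on success follows from the endpoint's definition and is not concealed. The proportions reaching TICI ≥2b, by aspiration and after an additional device, stand in the same list, so a low success rate would show beside the time. The endpoint is secondary and descriptive in a single-arm registry, with no speed threshold. At 80–90% success the illustrative shift is only about 3 to 6 min.

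This stands as a limit on size. It does not remove the point: a proportion and a median among successes do not give the share of all patients recanalized by a given time, which is what a claim of fast recanalization is about. Nor can the matter simply be left to the SAP, because the protocol itself names descriptive statistics as the method.

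On dated events the objection is stronger. The protocol does not say that deaths are censored; that is the usual behaviour of the named method. The safety endpoints and adverse events are also reported as occurrences, counts and percents. These keep patients who die in the denominator and are free of this bias. Four of the five safety endpoints are fixed at end of procedure, 24 h or discharge.

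A reader might infer that Kaplan-Meier would be applied to aspiration success with switches censored, which would inflate the success rate. The documents do not support this: 9.2.4 assigns descriptive statistics, success is reported directly as a proportion, and a date of onset describes adverse events rather than a procedural clock time.

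**Conclusion.** The point holds for recanalization time. As written, the speed result describes successes only, split by route, and cannot speak for all patients in whom aspiration was tried first. How far this matters depends on the success share, which the documents do not give: on the assumed distribution it is small at 90% success and large at 60% or below.

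The Kaplan-Meier point is minor. The likely excess is about 0.3 to 3.3 percentage points at 90 days under assumed mortality of 10–25%, and negligible at 24 h. What needs settling is that the synopsis and sections 9.2.3 and 9.2.7 offer two kinds of estimate for overlapping events.

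A reader might also infer from the observed-data rule in 9.2 that visit scores generally describe survivors only. That is wrong for the primary 90-day mRS: 9.2.1 does not treat death before 90 days as a missing outcome. For NIHSS and quality of life no value for death is stated, but whether to rank death as the worst category is a debatable choice, and there is no basis here for sizing an effect.

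**What to change.** Add to 9.2.4 a cumulative incidence curve of TICI ≥2b by first-line aspiration over all intent-to-treat patients, starting at groin puncture. Treat switch to another technique and end of procedure without TICI ≥2b as competing events. Report the proportion recanalized by fixed times, for example 30 and 60 min. Keep the median among successes, labelled as conditional on success and secondary.

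As a lesser change, for dated non-fatal events to 90 days replace the synopsis Kaplan-Meier estimate by the Aalen-Johansen cumulative incidence with death as competing event. Keep Kaplan-Meier for all-cause death. State how these curves relate to the counts and percents in 9.2.3 and 9.2.7. At most, show the number dead beside the NIHSS and quality-of-life summaries.

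The cost is wording in the protocol and SAP. The procedural times are already collected under 5.5, and event and death dates under Table 3 in 6.1.2, so no new data are needed. The only downside is a speed figure that may look less favourable.

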9.2.6. Supplemental Endpoints

Imaging endpoints:

- Difference of ASPECT scores in CT/MRI pretreatment vs. 24h
- In the subgroup of patients with additional perfusion CT (as per local standard of care): volume of saved brain tissue determined by predictive modeling

Health Economics:

- Device costs (standardized cost of all devices as well as human resources and medication used during index procedure)
- Hospital length of stay

Descriptive statistics will be provided for supplemental endpoints. Exploratory data analysis will be performed to assess the possible influence of treatment factors on health economic measures. Estimates of the group differences and their 95% confidence intervals will be calculated.

9.2.7. Analysis of Adverse Events:

All adverse events will be summarized by showing the number and percent of patients reporting the event. Events will also be reported by relationship to the procedure or device.

9.2.8. Interim Analysis and Early Stopping Rules

An interim analysis is planned after the first 50 patients enrolled have reached the 3 months follow-up for the purpose of assessing Effectiveness and safety tendencies. If interim analysis data are sufficient to demonstrate study success, then the trial enrollment will be terminated early. If interim analysis data indicate that study success is highly unlikely even if enrollment were to continue to a maximum sample size of 250, then the trial enrollment will be terminated early for futility. Otherwise, study enrollment will continue to a maximum sample size of n=250 and analysis will be performed when 90-day follow up visits are complete.

The decision to stop or continue the trial will be based on the overall assessment of risk and benefit by the steering committee, supported by the CEC. Safety interim analysis will be performed after one third and two thirds of the patients have been included.

10 Quality Control and Quality Assurance

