4.1. Study Design

This is a multi-center, single arm, prospective, observational registry of the SOFIATM/ SOFIATM PLUS Catheter in Europe. Consecutive patients presenting within 6 hours of symptom onset with an anterior circulation large vessel occlusion (LVO) acute ischemic stroke (within the internal carotid artery and internal carotid terminus, middle cerebral $-M_1/M_2$ segments) will be treated using aspiration thrombectomy as first intention and site routine practice. Devices received CE-mark and will be used according to the 'Instructions For Use'.

The follow-up visits will occur at 24 + - 12 hours, at patient discharge, and 90 + - 14 days post-procedure.

Furthermore the study design is adaptive, prospectively stating interim analyses with specified stopping rules, which allow for the possibility of the study to terminate early based on either a determination of study success or of the futility to continue further enrollment.

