10.4. Clinical Events Committee

The Clinical Events Committee (CEC) is made up of independent medical doctors who are not participants in the study. At the onset of the study, the CEC will establish explicit rules outlining the minimum amount of data required, and the algorithm followed in order to classify a clinical event. All members of the CEC will be blinded to the primary results of the trial. The CEC will meet regularly to review and adjudicate any clinical events, to evaluate their relationship to the de-

vice/procedure and to the study endpoints. The CEC will also review and rule on all deaths that occur throughout the trial. A CEC Charter, generated by the CEC membership will identify the frequency of meetings, identify criteria for early review safety, any additional criteria for stopping the study early and criteria for inactivating sites for excessive protocol deviations.

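### Stopping enrolment for success or futility after the 50-patient look conflicts with a study sized only for ±6-point precision

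*Protocol*

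**What the plan says.** Section 9.1 of the protocol describes the design as estimation: "Within a descriptive study, the number of participants required depends on the desired accuracy for observed frequencies". Its only quantitative basis is the width of the interval at 236 patients, with 95% confidence, given as follows: "size of ± 6.0% will be obtained for a attended frequency of mRS ≤ 2 at 90 days of 32,6" (in percent). The planned 250 allows for 5% loss to follow-up. Section 4.2 states the primary objective as observing the percentage of good outcomes.

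Section 9.2.8 places an interim analysis after the first 50 enrolled patients reach three months, to look at tendencies in effectiveness and safety. It then adds a consequence: "If interim analysis data are sufficient to demonstrate study success, then the trial enrollment will be terminated early". If success looks highly unlikely even at 250 patients, enrolment also ends, for futility. Otherwise it runs to 250. The decision itself is left to an "overall assessment of risk and benefit by the steering committee, supported by the CEC". Safety looks are planned after one third and two thirds of patients.

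Section 4.1 calls the design adaptive, "prospectively stating interim analyses with specified stopping rules". Section 9.2 requires all endpoints to be evaluated separately for the two catheters.

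**The concern.** A study whose purpose is to estimate a proportion to a chosen accuracy succeeds by reaching that accuracy. It has no result that could be shown early, because accuracy depends on how many patients are observed. Section 9.2.8 brings in the logic of a confirmatory trial, with success and futility, although sections 9.1 and 4.2 set up nothing to succeed or fail against. Section 4.1 says the rules are specified, but the protocol gives no reference rate, performance goal or boundary.

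The missing threshold is not the main point, since a statistical analysis plan could supply one. The main point is that no threshold repairs the conflict: once enrolment ends near 50 patients, the ±6 points that justified 250 are out of reach.

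Two things are at stake. The primary estimate could be reported with about twice the planned uncertainty. And because the stop would be triggered by the observed rate itself, the rate reported after a stop would be systematically off.

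**Working it through.** **Inputs.** Expected rate p = 0.326, target half-width ±6.0 points, n = 236, 250 planned, 5% loss (section 9.1). Interim at 50 followed patients (section 9.2.8). Enrolment over up to 42 months (section 2). Half-width formula: 1.96 × √(p(1 − p)/n), with p(1 − p) = 0.326 × 0.674 = 0.2197.

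**1. The protocol's own figure.** At n = 236: 1.96 × √(0.2197/236) = 5.98 points. This reproduces ±6.0. With 5% loss, 250 × 0.95 = 237.5 gives 5.96. The stated design is internally correct.

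**2. Precision after a stop at the interim.** At n = 50: 1.96 × √(0.2197/50) = 12.99 points, which is 12.99/5.98 = 2.2 times the planned half-width. With 16/50 observed, the Wilson interval runs from 20.8% to 45.8%.

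**3. Allowing for overrun.** The protocol does not say that enrolment pauses while the 50 are followed for three months. Assuming an even rate of 250/42 = 5.95 patients per month, about 3 × 5.95 = 18 more would be enrolled, 68 in all: 1.96 × √(0.2197/68) = 11.1 points. From 50 to 75 patients the half-width runs from 13.0 to 10.6 points.

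**4. By catheter.** The split between SOFIA and SOFIA Plus is not given. With an assumed 25/25 split of 50 patients: 1.96 × √(0.2197/25) = 18.4 points for each.

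**5. Relation to the safety looks.** One third of 250 is about 83 patients. A stop at 50 to 68 patients would come before either planned safety look.

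**6. Bias, illustration only.** The protocol gives no rule, so one is assumed: stop if the lower 95% limit exceeds 32.6%, which needs at least 24/50 (exact or Wald limit). Exact binomial enumeration with no overrun and no futility stop gives the table below. If a study that does not stop goes on to 250, the interim 50 carry weight 50/250, so the average bias over all outcomes is 0.8 × P(stop) × (mean rate if stopped − true rate).

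| True rate | P(stop) | Mean rate if stopped | Average bias over all outcomes |
|---|---|---|---|
| 32.6% | 1.7% | 49.6% | 0.8 × 0.0168 × 0.170 = +0.2 points |
| 40% | 15.6% | 50.8% | 0.8 × 0.156 × 0.108 = +1.3 points |

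A looser assumed rule, stopping at 17/50 or more (observed rate above 32.6%), stops 47% of the time at a true rate of 32.6%, with a mean of 38.3%. At a true 40% it stops 84% of the time, with a mean of 42.0%. Across the rules and true rates examined, the excess among stopped studies runs from about 2 to 17 points. If 18 unselected overrun patients are added, that excess shrinks by 50/68 = 0.74. A futility stop works in the opposite direction.

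**The case against.** The best defence is that the protocol's aims are mixed. Section 9.2 speaks of supporting a demonstration, section 4.4 wants to show results similar to published ones, and sections 4.3 and 9.2.8 treat 250 as an upper limit. A success criterion may sit in an analysis plan, and section 10.4 leaves further stopping criteria to the CEC charter. The steering committee also weighs risk and benefit overall, so a stop need not be automatic. This answers the complaint that no threshold is given. It does not answer the conflict with section 9.1, because neither a threshold nor committee discretion narrows the interval at 50 to 68 patients. Discretion also sits poorly with rules that section 4.1 calls specified.

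Three stronger readings are tempting and should not be drawn.

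- **Inflated type I error.** Section 9.2 says "All statistical tests will be two-tailed with a significance level of 0.05", and a reader might infer that an unadjusted second look inflates the error. That needs a hypothesis tested at both looks. The protocol states no null rate for the primary endpoint, so there is no error rate to inflate, and interim error control is commonly left to an analysis plan.
- **A large bias as an established feature.** The excess of roughly 11 points at a true rate of 40% is conditional on a stop that happens 16% of the time under an assumed rule. Section 9.1 gives 32.6% as an expected frequency, not as a goal to beat. Averaged over all outcomes the bias is about 1 point or less in that illustration.
- **A contradiction in the CEC's role.** Section 10.4 says "All members of the CEC will be blinded to the primary results of the trial", while section 9.2.8 has the CEC support the stopping decision. The steering committee decides, and the CEC adjudicates events, their relation to device or procedure, and deaths. It can inform the risk side while blinded, so the two sections can be read together.

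**Conclusion.** The conflict between sections 9.1 and 4.2 on one side and section 9.2.8 on the other is real and lies in the protocol itself. A stop for success or futility at the 50-patient look would leave a half-width of about ±13 points, or about ±11 with overrun, against the ±6 that justifies the sample size. These figures rest on the protocol's 32.6% and on the Wald formula that reproduces its own calculation. The ±11 also assumes even enrolment of 250 over 42 months with no pause.

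The direction of the bias is clear for any rule that acts on the observed rate: upward after a success stop, downward after a futility stop. Its size cannot be fixed from the protocol, and the figures above only illustrate it. The point does not extend to a type I error claim or to a contradiction in the CEC's blinding.

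**What to change.** In section 9.2.8, remove the stops for success and for futility. Keep the 50-patient look as a descriptive report, which matches its stated purpose of assessing tendencies. Keep the safety looks at one third and two thirds, and state that enrolment continues to 250 unless stopped for safety. In section 4.1, delete or rewrite the adaptive paragraph to agree. It would help to add that the CEC's input to any stopping decision is limited to safety.

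If the sponsor does want an early effectiveness stop, the alternative is to state the criterion and rewrite section 9.1 around it, accepting that ±6 points is then no longer guaranteed. That is the larger change.

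The recommended change costs protocol wording and gives up the option to finish early, an option the present precision target already rules out.
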